### Secondary outcomes

Retention in care: A participant will be considered as retained in care if they have a documented ART clinic or refill visit at the study facility or a referral facility between 22 and 30 weeks after enrolment. Evidence of viral suppression up to week 40 is also considered as retention in care.

Engagement in care: A participant will be considered as engaged in care if they reported regular ART intake between 22 and 30 weeks after enrolment. This documentation of

regular ART intake can be taken from information provided by the participant during the study visit, retrieved from the week 30 register review, or from tracing information provided by the participant. Evidence of viral suppression up to week 40 is also considered as engagement in care.

Disengagement from care: A participant will be considered as disengaged from care if not engaged in care but the participant was verified to be alive after week 22 during patient tracing.

Lost to follow-up: A participant will be considered lost to follow-up if there is no documentation of a clinic visit between weeks 22 and 30 after enrollment and no information about the participant was found through tracing.

Non-traumatic mortality, SAEs, and AESIs: See below for definition. Any of these defined events occurring during the first 30 weeks after enrolment will be considered.

Incidence of TB disease: Diagnosis of TB between 28 days and 30 weeks after enrolment.

HIV viral suppression: As a sensitivity analysis of the primary outcome, we will consider three different thresholds for defining viral suppression (<20 copies/mL; <100 copies/mL; <1000 copies/mL). The VL tests must be done as for the primary endpoint between weeks 22 and 40 after enrollment.

Note that VL results measured using DBS have a detection limit of >100 copies/mL and therefore will not be included in the reporting of the threshold of <20 copies/mL or <100 copies/mL.

ART initiation: Any record of an individual starting ART within 7 and within 28 days after enrolment. This information is documented in the study database in a dedicated format the time of ART initiation if observed by the study team or retrospectively based on clinic records. The source can be the 26 week study visit, any register review, or the tracing data.

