#### 4.1.2 Secondary and safety endpoints

- Retention in care 26 (22 – 30) weeks after enrolment, defined as a documented ART clinic visit between 22 and 30 weeks after enrolment
- Engagement in care 26 (22 – 30) weeks after enrolment, defined as reporting regular ART intake, irrespective if a documented visit took place between 22 and 30 weeks after enrolment
- Disengagement from care 26 (22 – 30) weeks after enrolment, defined as non-engaged in care but reached through patient tracing
- Lost to follow-up 26 (22 – 30) weeks after enrolment, defined as non-retained in care and not reached through tracing
- Non-traumatic mortality, SAEs, and AESIs (see section 7.1.3 for definition) during the first 30 weeks after enrolment
- Incidence of TB disease (microbiologically confirmed and/or clinical diagnosis) during the first 30 weeks after enrolment, defined as any TB diagnosis after enrolment not classified as prevalent TB at enrolment (see definition below under exploratory endpoints)
- HIV viral suppression at 26 (22 – 40) weeks using different thresholds (<20 copies/mL; <100 copies/mL; <1000 copies/mL)
- ART initiation within 7 and within 28 days after enrolment

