## 6.1 Outcome definitions

Here we define outcomes for analysis. Table 1 provides the analysis windows for the occurrence of the outcomes.

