### Primary outcome

The study visit for primary outcome assessment was scheduled together with the routine 6 month ART refill visit. Study staff tried to ensure that a VL was measured for the assessment of the study primary endpoint. If VL was not successfully measured or a study visit did not occur, participants were traced in order to obtain the outcome assessment.

Viral suppression is defined as a HIV VL <400 copies/mL during the defined analysis window of 154-280 days (Table 1). The viral load was obtained from routine laboratory reports at study facilities, from laboratory reports of referral facility in case of transfer out, or from dried blood spot (DBS) sample for participants without documented clinic visit but found during home visit tracing.

If more than one VL is available for a participant during this window, any value meeting the definition of viral suppression will be considered and defined as the participant achieving the primary endpoint.

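### SAP 6.1 counts viral suppression up to week 40 as retention in care with no clinic visit and no stated reason, whereas protocol 4.1.2 defines retention by attendance in weeks 22–30

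*SAP*

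**What the plan says.** Protocol 4.1.2 gives retention in care as "defined as a documented ART clinic visit between 22 and 30 weeks after enrolment". SAP 3.1 repeats this and attributes it to the protocol.

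SAP 6.1 opens with "Here we define outcomes for analysis", so its definitions are the operative ones. It accepts a clinic or refill visit, at the study facility or a referral facility, in weeks 22–30. It then adds "Evidence of viral suppression up to week 40 is also considered as retention in care".

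Three neighbouring definitions matter:

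- **Engagement.** The protocol bases it on reported regular ART intake, "irrespective if a documented visit took place between 22 and 30 weeks after enrolment". SAP 6.1 adds a matching sentence: "Evidence of viral suppression up to week 40 is also considered as engagement in care".
- **Loss to follow-up.** In the protocol it is "defined as non-retained in care and not reached through tracing". In SAP 6.1 it requires "no documentation of a clinic visit between weeks 22 and 30 after enrollment and no information about the participant was found through tracing".
- **Primary outcome.** Success is a viral load below 400 copies/mL on days 154–280. The result may come "from dried blood spot (DBS) sample for participants without documented clinic visit but found during home visit tracing".

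SAP 6.2 tests retention for superiority in the ITT population. The SAP revision history does not mention retention. SAP 3.7 makes only a general remark that analysis windows are wide.

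**The concern.** Accepting refill visits and referral facilities clarifies what counts as a visit. The suppression sentence does something different: it lets a laboratory result stand in for attendance. The protocol already has an endpoint for people who take ART without a recorded visit, namely engagement. With the same sentence attached to both endpoints, the distinction between them blurs.

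Attendance has its own place in this trial. Protocol 2.3 argues that deferring ART may cause attrition from care, and protocol 9.2.2 singles out retention and ART initiation for superiority testing. SAP 4.1 makes no multiplicity adjustment and interprets results partly by their consistency across related outcomes. If retention contains the primary successes by definition, part of that consistency is built in. A reader of the final report could also take the retention result as a statement about clinic attendance when it is partly a statement about viral load.

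**Working it through.** **The plan's own figure.** The sample size reproduces, although this point does not rest on it. With 75% in both arms, a margin of 0.10, one-sided alpha 0.025 and power 80%:

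n = (1.96 + 0.842)² × (2 × 0.75 × 0.25) / 0.10² = 294.3, so 295 per arm and 590 in total. Retention was not used for sizing.

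**The definitions side by side.** I read suppression in the retention sentence as the primary definition (below 400 copies/mL, days 154–280). The sentence itself states neither a threshold nor a lower time limit.

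| Participant | Protocol 4.1.2 and SAP 3.1 | SAP 6.1 |
|---|---|---|
| Visit in weeks 22–30, any viral load | Retained | Retained |
| No visit in weeks 22–30, suppressed home blood spot in weeks 31–40 | Not retained | Retained |
| No visit in weeks 22–30, clinic visit in weeks 31–40, suppressed | Not retained | Retained |
| No visit in weeks 22–30, clinic visit in weeks 31–40, not suppressed | Not retained | Not retained |
| Transferred out, suppressed report from the referral facility, no visit date on record | Unclear | Retained |
| No visit and no suppressed result | Not retained | Not retained |

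Two consequences follow:

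1. Primary success is suppression on days 154–280. SAP retention is a visit on days 154–210 or suppression up to day 280. The first set lies inside the second.
2. Someone who attends unprompted at week 33 with a suppressed result, and about whom tracing finds nothing, meets SAP 6.1's definitions of both retained and lost. The protocol's non-retained condition rules this out. The case should be rare, because people without a viral load in weeks 22–30 are traced.

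**How far the result can move.** Let s be the proportion of an arm that is suppressed with no visit in weeks 22–30. Then:

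risk difference (SAP 6.1) = risk difference (visit-only) + s(ART first) − s(TB results first).

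The documents do not give s. The figures below use assumed rates with 295 per arm.

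- *Dilution.* Take visit-only retention of 80% v 70%, a 10-point difference with about 80% power. If a fraction f of non-attenders in each arm is suppressed, the difference becomes 10 × (1 − f). For f = 10%, 20% or 40% this is 9, 8 or 6 points, with power of about 75%, 68% or 53%. If f is 20% in ART first and 40% in control, the rates are 84% v 82%: 2 points, power about 9%.
- *Counts.* Visit-only 260/295 v 236/295 is a difference of 8.1 points (Wald 95% CI 2.3 to 14.0). Superiority is lost once a net 8 controls are reclassified as retained (260 v 244).
- *Opposite direction.* With equal attendance a, the SAP 6.1 gap is (1 − a) × the difference in suppression among non-attenders. For a from 75% to 90% and a 20-point difference, the gap is 0.25 × 20 = 5 down to 0.10 × 20 = 2 points. Superiority was then declared in 14–40% of simulated trials. When the suppressed share is equal in the two arms, the rate is 2.5% under both rules.

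**The case against.** The best defence is that few people are affected. The endpoint viral load is scheduled with the routine six-month refill, so a success measured at a clinic visit in weeks 22–30 is retained under either rule. This stands, and it limits the point.

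Second, the visit-only rule has its own weakness. The control arm starts ART later while the window runs from enrolment, so late attendance in controls is plausible. If attendance by week 40 is 80–90% in both arms but 5 extra points of controls attend only in weeks 31–40 (assumed), visit-only retention shows superiority in 31–45% of simulated trials. Under SAP 6.1, with 75–90% of those late attenders suppressed, it does so in 4–7%. This also stands. It is a reason to show both versions, but not to replace the protocol's endpoint without comment.

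Third, for transfers out, protocol 6.11 describes obtaining a viral load report from the referral facility, not visit dates, and the register review covers the study facility. A viral load may be the only evidence of care elsewhere. That is a plausible reason for the sentence, but the SAP does not give it.

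Fourth, part of this will be visible anyway. SAP 5.4 reports study visits by arm and summarises tracing, and SAP 6.2 reports the share of primary outcome data that came from tracing. Neither gives a visit-only risk difference with a confidence interval.

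**Conclusion.** The conflict is real and rests on the wording alone: SAP 6.1 differs from protocol 4.1.2 and from SAP 3.1, gives no reason, and plans no analysis under the protocol's rule. It can change the reported retention result. It does not touch the primary conclusion or the sample size. Its size is unknown, because it depends on how many participants are suppressed with no visit in weeks 22–30.

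Three stronger readings are not supported:

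- At the planned 75% suppression, 0.75 × 295 = 221 per arm would be retained by definition, and a reader might take that as the size of the problem. It is not, because successes who also attended in weeks 22–30 are retained under the protocol too.
- The simulated superiority rates might be read as inflated type I error. They are power to detect an assumed difference in the SAP-defined endpoint, and nothing in the documents supports the assumed differences between arms.
- A reader might infer that the Malawi detection-limit rule in SAP 6.2 now also governs retention. The SAP states that rule for the primary analysis only and does not say whether it carries over.

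**What to change.** 1. In SAP 6.1, test retention for superiority as a documented ART clinic or refill visit, at the study facility or a referral facility, on days 154–210. This uses visit data the SAP already calls for. Note that referral-facility visit dates may be incomplete.
2. Report the present SAP 6.1 version (that visit, or viral load below 400 copies/mL on days 154–280) as a labelled sensitivity analysis with risk difference and 95% CI. State that it departs from protocol 4.1.2 and why.
3. Where dates exist, describe by arm the number and percentage with any documented visit on days 154–280 whatever the viral load, and the number with unknown dates. Attach no decision rule, because dates in weeks 31–40 may be incomplete: protocol 6.8 does not require uncomplicated visits to be recorded.
4. Keep the suppression sentence in engagement only, and restore the non-retained condition in the loss-to-follow-up definition.

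The cost is SAP wording and two extra table rows, settled before outcomes are analysed by arm. The price of the visit-only rule is greater sensitivity to late attendance, which items 2 and 3 make visible.

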## Endpoints

As per the protocol, the primary endpoint of the trial is:

- HIV viral suppression <400 copies/mL 26 (22 – 40) weeks after enrolment (obtained from routine laboratory reports at study facility, from laboratory reports of referral facility in case of transfer out, or from dried blood spot (DBS) sample for participants without documented clinic visit but found during home visit tracing)

As per the protocol, the secondary endpoints of the trial are:

- Retention in care 26 (22 – 30) weeks after enrolment, defined as a documented ART clinic visit between 22 and 30 weeks after enrolment
- Engagement in care 26 (22 – 30) weeks after enrolment, defined as reporting regular ART intake, irrespective if a documented visit took place between 22 and 30 weeks after enrolment
- Disengagement from care 26 (22 – 30) weeks after enrolment, defined as non-engaged in care but reached through patient tracing
- Lost to follow-up 26 (22 – 30) weeks after enrolment, defined as non-retained in care and not reached through tracing
- Non-traumatic mortality, SAEs, and AESIs (see section 7.1.3 for definition) during the first 30 weeks after enrolment
- Incidence of TB disease (microbiologically confirmed and/or clinical diagnosis) during the first 30 weeks after enrolment, defined as any TB diagnosis after enrolment not classified as prevalent TB at enrolment (see definition below under exploratory endpoints)
- HIV viral suppression at 26 (22 – 40) weeks using different thresholds (<20 copies/mL; <100 copies/mL; <1000 copies/mL)
- ART initiation within 7 and within 28 days after enrolment

As per the protocol, the exploratory endpoints of the trial are:

- Clinical characteristics of participants with non-traumatic hospitalizations and deaths in PLHIV with presumptive TB
- Prevalence of active TB diagnosed at enrolment, defined as TB diagnosed clinically or microbiologically through the TB investigations initiated at enrolment and completed up to a maximum of 28 days after enrolment.

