**Table 1. Nominal activities and permitted windows.**

Activity/endpoint	Nominal activity week	Nominal activity day	Protocol defined window, weeks	Protocol defined window, days
ART initiation	1	7	<1	<7
ART initiation	4	28	<4	<28
Study visit	26	182	22 - 30	154 - 210
TB Incidence	<30	<210	4 – 30	28 – 210
Safety events	<30	<210	0 - 30	0 - 210
Register review	>=30	>=210	>=30	>=210
Tracing	31-40		31 - 40	217 - 280
Primary outcome	22 - 40	154 - 280	22 – 40	154 – 280

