Death due to non-trauma	“While alive” approach	Those with the IE prior to VL measurement are included as failures; those with the IE after their VL measurement are included with their endpoint.
Death due to trauma	“While alive” approach	If the endpoint is measured prior to the IE, will be included.
Death due to trauma	“Principal stratum” approach	If the endpoint is not measured prior to the IE, these individuals will be excluded assuming the IE is independent of treatment allocation.

Lost to follow-up	“Composite” approach	No viral load measured. Those with the IE would be considered to have failed treatment and are therefore included as part of the endpoint definition above.
-------------------	----------------------	---

[1] Intercurrent events are post-randomization events that affect either the interpretation or existence of the outcome data associated with the clinical question of interest. . [2] Intercurrent events are post-randomization events that affect either the interpretation or existence of the outcome data associated with the clinical question of interest. [3] The case where individuals had blood drawn for a viral load test, but the test was invalid or failed will be handle with imputation if numbers allow.

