### **Secondary outcomes analysis**

All secondary binary outcomes will be estimated as with the primary outcome and summarized with risk differences, risk ratios and 95% confidence intervals.

The secondary outcome of HIV viral suppression at different thresholds will be analyzed similar to the primary outcome - as a non-inferiority comparison followed by superiority if non-inferiority is established but no sensitivity analyses or effect modification will be done.

The secondary endpoints of retention in care, engagement in care, disengagement from care, lost to follow-up, and ART initiation within 7 or 28 days after enrollment will be assessed for superiority in the ITT population.

Non-traumatic mortality, hospitalizations, SAEs, AESIs and incidence of TB will be summarized descriptively as events are expected to be rare.

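### SAP 6.1 can class one participant as retained, engaged and lost to follow-up at once, and Tables 2a/2b use the same label for a different count

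*SAP*

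**What the plan says.** The SAP uses the term lost to follow-up in three places.

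- **SAP 6.1, Secondary outcomes.** This section sets out the definitions used for analysis. "A participant will be considered lost to follow-up if there is no documentation of a clinic visit between weeks 22 and 30" is the first condition. The second is that "no information about the participant was found through tracing".
- **SAP 3.1, Endpoints, repeating protocol 4.1.2.** Loss is "defined as non-retained in care and not reached through tracing".
- **SAP Tables 2a and 2b.** Loss is an intercurrent event of the primary estimand, handled as a composite: "No viral load measured. Those with the IE would be considered to have failed treatment".

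Two neighbouring rules matter. For retention, SAP 6.1 adds: "Evidence of viral suppression up to week 40 is also considered as retention in care". It adds the same for engagement. The primary outcome uses any viral load "during the defined analysis window of 154-280 days", that is, weeks 22-40.

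On reporting, SAP 6.2 summarises the intercurrent events of Tables 2a/2b by number and percentage. For the secondary outcome it states that "lost to follow-up, and ART initiation within 7 or 28 days after enrollment will be assessed for superiority in the ITT population". SAP 4.1 makes no multiplicity adjustment.

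**The concern.** SAP 6.1 moves the boundary of retention from week 30 to week 40 for anyone with a suppressed viral load, but leaves the boundary of loss at week 30. Under the protocol's own retention definition (a documented ART clinic visit in weeks 22-30), the visit condition in 6.1 and the protocol's non-retained condition amount to the same thing. They part once retention is widened. Because 6.1 names the visit rather than retention status, the widening never reaches the loss rule, and two outcomes that should exclude each other can overlap.

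Two things are at stake. First, loss to follow-up is compared between arms, and returning late to clinic is something that the timing of ART could influence. A rule that calls some late returners lost mixes delay with disappearance. Second, the report will contain two counts under one name: participants without a viral load (Tables 2a/2b) and participants meeting the 6.1 rule.

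**Working it through.** **The plan's own figure.** The documents give no rate, count or power for loss to follow-up. The only stated figure nearby is the sample size (SAP 3.3), with 75% suppression in both arms, a 10-point margin, one-sided alpha 0.025 and power 80%:

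n = (1.960 + 0.842)² × 2 × 0.75 × 0.25 / 0.10² = 294.3, so 295 per arm and 590 in total. This reproduces the plan. I use 295 per arm below.

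**The definitions side by side.** I crossed three facts: a clinic visit in weeks 22-30 (yes/no), the viral load (none; weeks 22-30 or 31-40; suppressed or not), and tracing information (yes/no). I then applied each wording. For SAP 3.1/protocol, non-retained is read with retention as SAP 6.1 defines it, and the two tracing conditions are treated as equivalent. The wordings disagree only here:

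| Visit wk 22-30 | Viral load | Tracing information | Retained (6.1) | Lost: 6.1 | Lost: 3.1/protocol | Lost: Tables 2a/2b |
|---|---|---|---|---|---|---|
| No | Wk 31-40, suppressed | No | Yes | **Yes** | No | No |
| No | Wk 31-40, unsuppressed | No | No | **Yes** | Yes | No |
| No | None | Yes | No | No | No | Yes |
| Yes | None | Either | Yes | No | No | Yes |

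Row 1 is the contradiction: primary-endpoint success, retained, engaged and lost. In row 2 the primary endpoint is observed as a failure, yet the participant is lost under both 6.1 and the protocol wording. Rows 3 and 4 show why the Tables 2a/2b count will differ from the 6.1 count.

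**Who can fall in rows 1 and 2.** Protocol 6.11 traces everyone without a study-facility viral load in weeks 22-30. Dried blood spots and referral-facility reports are obtained through that tracing, so they count as tracing information. What remains is a participant who comes back to the study facility unprompted in weeks 31-40 and about whom tracing yields nothing.

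**Illustrative size.** These are assumptions: true loss of 5-15%, and 1% or 3% of an arm mislabelled (295 × 0.01 ≈ 3 and 295 × 0.03 ≈ 9 participants).

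*Equal mislabelling in both arms.* The risk difference is unbiased and the error rate stays at 5%. Power = Φ[(|p1 − p2| − 1.96 × SE0) / SE1], where SE0 = √(2p̄(1 − p̄)/295) and SE1 = √([p1(1 − p1) + p2(1 − p2)]/295):

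- 10% v 5%: (0.05 − 1.96 × 0.0217)/0.0216 gives 64%
- 11% v 6% (1 point added to both): 59%
- 13% v 8% (3 points added to both): 51%

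*Mislabelling in one arm only, no true difference.* The risk difference shifts by the mislabelled fraction d. The chance of a significant result is Φ(−1.96 + d/SE1) + Φ(−1.96 − d/SE1):

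| True loss | d = 1 point | d = 3 points |
|---|---|---|
| 5% | 8.3% | 31.6% |
| 10% | 6.8% | 20.8% |
| 15% | 6.3% | 16.6% |

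One-sided mislabelling is the extreme case. Nothing in the documents shows that it would occur.

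**The case against.** **The group is narrow.** A late returner is still due for tracing by phone and home visit, and relatives or friends are asked if the participant cannot be found. To be mislabelled, the participant must have attended the study facility in weeks 31-40 and yet yield no information from any of this. Staff might also record a late result found in the registers as tracing information. This objection stands, and it is why the point is minor. A reader might see a hole in SAP Table 1, where the visit window closes on day 210 and tracing opens on day 217. But eligibility for tracing depends on having no viral load in weeks 22-30, so someone returning on day 213 is not outside its reach.

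**An unsuppressed late returner meets the protocol's definition.** This is correct. Such a person is non-retained and not reached, so calling them lost is not a departure by the SAP. Removing them is a clarification that goes beyond the protocol and should be declared as one.

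**Tables 2a/2b do not compete with 6.1.** A reader might infer that the SAP holds two rival definitions of the secondary outcome. It does not. The table row handles a missing primary endpoint, and the tables' endpoint row speaks of loss without a viral load, which treats the two ideas as separable. What survives is the shared label on two reported counts.

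**The size cannot be estimated.** A reader might model visit times. For example, attendance centred on day 182 with SD 14, 21 or 28 days puts 2.1%, 8.7% or 15.4% on days 211-280. That describes late attendance, not late attendance with failed tracing. Likewise, dividing an assumed 1-3% mislabelled by an assumed 5-10% true loss gives an inflation of 10-60%, but this is only a ratio of two assumptions.

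**Conclusion.** The concern holds as an internal inconsistency of minor severity. The SAP 6.1 rule uses a week 22-30 visit where the protocol and SAP 3.1 use retention status. Since 6.1 has itself widened retention and engagement to week 40, a literal reading makes one participant retained, engaged and lost. Loss to follow-up can therefore be miscounted in an ITT superiority comparison.

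The documents do not support the stronger statement that it is miscounted, or that the comparison is biased. They give no counts, equal mislabelling leaves the risk difference unbiased, and unequal mislabelling is only a possibility. The primary endpoint is unaffected, because a viral load in days 154-280 is used whatever the loss label. The power and error figures above rest on assumed rates and show only the order of effect.

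**What to change.** In SAP 6.1, define lost to follow-up by three conditions, all required:

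1. not retained in care as 6.1 defines retention, which restores the protocol's condition;
2. no viral load result from any source in days 154-280;
3. no information through tracing.

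Condition 1 alone removes the contradiction in row 1 of the table. Condition 2 also removes row 2. The SAP should state that excluding participants with an unsuppressed late viral load is a clarification beyond the protocol wording.

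The rule should rest on viral load and retention variables, which are already needed for other outcomes, and not on clinic visits in weeks 31-40. Protocol 6.8 does not require uncomplicated visits to be documented, and the mandatory final register review in protocol 6.10 is at week 30, so systematic capture of later visits is not promised.

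In Tables 2a/2b, rename the intercurrent event 'No VL result in days 154-280', so that the intercurrent-event summary and the secondary endpoint in SAP 6.2 do not report different counts under one name.

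The cost is a few lines of SAP wording and one derivation change. No new data are needed and the sample size stays at 295 per arm. The downside is a slightly smaller count of participants lost.

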## 4.3 Analysis populations

As per the protocol (2), all analyses will be done by the trial statistician using R (the R Foundation for Statistical Computing) or Stata (version 18, Stata Corporation, Austin/Texas, USA). Analysis will follow CONSORT guidelines. Primary analyses for the non-inferiority comparison will be performed on both the ITT and per protocol (PP) sets (3).

Our approaches for the primary outcome are further detailed in the context of the estimands framework in Tables 2a and 2b (4).

For secondary outcomes related to VL (achieving viral suppression defined by other thresholds), we will employ similar methods as for the primary outcome (both superiority and non-inferiority comparisons).

For the remaining secondary outcomes, we will employ similar methods as for the primary outcome but under the superiority comparison only.

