We will conduct a planned subgroup analysis by country. Effect estimates of the primary outcome will be presented descriptively by subgroup. Potential effect modification of the primary outcome by ART status will be assessed by including interaction term between arm and the corresponding variable in the model. If the interaction term is found to be

significant ( $p<0.1$ ), effect estimates will be summarized descriptively by subgroup. The study is not powered for these pre-planned subgroup analyses so all results will be considered exploratory.

Given that VLs were done through the routine health system, in Malawi, some DBS tests were done on platforms with a limit of quantification at 839 copies/mL (Abbott m2000/real time) or 883 copies/mL (Panther Hologic). After conferring with experts, we have concluded to consider these tests as suppressed at the limit of 400 copies/mL for the primary analysis if the PCR target was not detected (as opposed to target detection but not quantifiable). As a sensitivity analysis of the primary outcome, we will consider these as not suppressed.

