### **6.3 Missing data**

Missing baseline and outcome data will be summarized by study arm. Where applicable, percentages will be of non-missing values.

In the case of missing VL for the primary endpoint, when no information is available, the participant is considered to have failed (see Table 2a and 2b). However, in the case where a VL result was not available, but information about ART refills is available, we will consider using multiple imputation in a sensitivity analysis if the numbers of these cases is sufficient to warrant the additional complexity.

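### The SAP sets aside every DBS result at the <20 and <100 copies/mL thresholds, although quantified DBS values are known failures there, and does not say how DBS-only participants are counted

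*SAP*

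**What the plan says.** SAP section 6.1 (Secondary outcomes) defines viral suppression at <20, <100 and <1000 copies/mL as a sensitivity analysis of the primary outcome. It then gives the DBS detection limit as above 100 copies/mL and says that DBS results "therefore will not be included in the reporting of the threshold of <20 copies/mL or <100 copies/mL". It makes no exception for DBS results with a quantified value.

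These thresholds carry formal comparisons. SAP 6.2 (Secondary outcomes analysis) has them analysed "as a non-inferiority comparison followed by superiority if non-inferiority is established but no sensitivity analyses or effect modification will be done". SAP 4.3 likewise carries over the primary-outcome methods to them.

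DBS results arise in two ways. SAP 6.1 (Primary outcome) describes a "dried blood spot (DBS) sample for participants without documented clinic visit but found during home visit tracing". SAP 6.2 (Primary outcome analysis) adds that "in Malawi, some DBS tests were done on platforms with a limit of quantification at 839 copies/mL", or 883 copies/mL on a second platform, and says that viral loads were done through the routine health system.

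For the primary endpoint, SAP 6.3 states: "In the case of missing VL for the primary endpoint, when no information is available, the participant is considered to have failed". Tables 2a and 2b say the same of participants lost to follow-up without a viral load. No sentence says whether a participant whose only result is a DBS stays in the <20 and <100 denominators and, if so, with what outcome.

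**The concern.** The detection limit is a sound reason for not placing a below-limit DBS relative to 20 or 100 copies/mL. It is no reason to discard a DBS that returned a number. If the DBS limit is above 100 copies/mL, every quantified DBS value is a failure at both thresholds. So the DBS results that can be classified are all failures, and the rule sets these aside together with the ones that cannot be classified.

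What follows depends on a step that the SAP leaves open:

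- **DBS-only participants leave the denominator.** A traced participant with a high DBS value drops out, while an untraced participant stays in as a failure.
- **DBS-only participants count as having no viral load, hence failed.** Known failures stay, but everyone with a below-limit DBS is recorded as a failure without evidence.

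At stake are two secondary non-inferiority comparisons meant to test how robust the primary result is to the threshold. They may not use the same population as the <400 analysis. The SAP plans no sensitivity analysis that would show the effect, and the choice between the handlings could be made after the data are seen.

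**Working it through.** **Plan's own figure.** SAP 3.3 gives 75% suppression, a 10-point margin, one-sided alpha 0.025 and 80% power. With equal arms, n = (1.960 + 0.842)² × 2 × 0.75 × 0.25 / 0.10² = 294.3, so 295 per arm, as stated; power at 295 is 80.1%. This applies to <400 only. The documents give no figure for <20 or <100.

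**Inputs for the check.** 295 per arm is from SAP 3.3. The 10-point margin at <20 and <100 is assumed, because SAP 6.2 carries over the primary approach and names no other margin. The documents give no DBS numbers, so all DBS counts below are assumptions.

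**Formulas.** In an arm of N = 295, let f be participants with only a quantified DBS (failures), b those with only a below-limit DBS, and s those suppressed on a non-DBS viral load. The proportion suppressed is then:

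- Handling 1, DBS-only participants leave: s / (N − f − b)
- Handling 2, DBS ignored, no viral load, failure: s / N
- Handling 3, quantified DBS kept as failures, below-limit DBS coded suppressed: (s + b) / N

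If below-limit DBS are instead coded not suppressed, handling 3 becomes s / N, the same as handling 2. The risk difference (RD) is ART first minus TB results first. The lower bound is RD − 1.96 × √[p₁(1−p₁)/n₁ + p₂(1−p₂)/n₂], unadjusted.

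**One case in full.** f = 30 vs 15, b = 15 in each arm, s = 191 vs 206 (ART first vs TB results first).

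- Handling 1: 191/250 = 76.4% and 206/265 = 77.7%; RD −1.3, lower bound −8.6.
- Handling 2: 191/295 = 64.7% and 206/295 = 69.8%; RD −5.1, lower bound −12.6.
- Handling 3: 206/295 = 69.8% and 221/295 = 74.9%; RD −5.1, lower bound −12.3.

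**All cases.** Entries are RD (lower bound) in percentage points.

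| Case (ART first vs TB results first) | Handling 1 | Handling 2 | Handling 3 |
|---|---|---|---|
| A. Equal arms: f 15, b 15, s 206 in each | 0.0 (−7.1) | 0.0 (−7.4) | 0.0 (−7.0) |
| B. f 30 vs 15; b 15 in each; s 191 vs 206 | −1.3 (−8.6) | −5.1 (−12.6) | −5.1 (−12.3) |
| C. f 15 vs 30; b 15 in each; s 206 vs 191 | +1.3 (−5.9) | +5.1 (−2.5) | +5.1 (−2.1) |
| D. f 15 in each; b 30 vs 15; s 191 vs 206 | −1.3 (−8.6) | −5.1 (−12.6) | 0.0 (−7.0) |

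**Reading the table.**

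- Case A: the RD does not move. The reported level does: 206/265 = 77.7%, 206/295 = 69.8% or 221/295 = 74.9%.
- Case B: dropping DBS-only participants puts the lower bound inside the margin. Keeping the known failures puts it outside, however below-limit DBS are coded.
- Case C: the same imbalance reversed. Dropping now understates ART first.
- Case D: handling 2 alone misses the margin, while coding below-limit DBS as suppressed meets it. Here the data cannot settle the question, and a single reported figure would hide that.

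**The case against.** The strongest reply is that the SAP sets aside results, not participants. If the primary methods carry over in full, a participant whose DBS is ignored has no viral load and counts as failed, so no known failure is lost. The rule also acts on assay type, not on outcome. Under Protocol 6.11, tracing is triggered by having no viral load in weeks 22 to 30, and venous blood is taken where possible, so DBS-only participants may be a subset of those traced. Some Malawi DBS tests came from routine care. The endpoints are secondary, and SAP 6.2 will report how much primary-outcome information came from tracing.

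Most of this stands, and it limits the point. Three stronger conclusions that a reader might draw are not supported:

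- **That the <20 and <100 analyses do lose known failures selectively.** This holds only if DBS-only participants leave the denominator, which the SAP does not state.
- **That the comparison is biased, or biased towards ART first.** A shift in the RD needs DBS use or results to differ between arms, and the documents do not show that. Protocol 11.2 expects pre-ART attrition to be lowest in the ART-first arm, which would point, if anywhere, towards case C.
- **That power falls from 80% to 71%.** Losing 20% of participants leaves 236 per arm and 70.8% power at 75% suppression, but 75% is the <400 design rate. If 80% of those remaining were suppressed, power at 236 would be about 77.5%. SAP 3.3 says that secondary endpoints were not considered in the sample size, so there is no stated power to lose.

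The reply does not rescue the rule. The no-viral-load reading keeps the known failures only by also failing every below-limit DBS, and the stated reason still does not cover quantified values.

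**Conclusion.** The point holds in limited form. The exclusion at <20 and <100 is wider than its stated reason, and the handling of DBS-only participants is undefined. Both available handlings are unsatisfactory: one may lose known failures, the other miscounts below-limit DBS. Either can distort these two non-inferiority comparisons in either direction when the arms differ in DBS use or results. With equal arms only the suppression level shifts.

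The size is unknown because the DBS share is not given. The cases show only that an imbalance of 15 participants per 295 can move the lower bound by about 4 points (−8.6 against −12.6) and change the conclusion. They rest on assumed counts, an unadjusted analysis and the 10-point margin carried over. The primary <400 endpoint and the <1000 threshold are not touched by this sentence, so the trial's main conclusion does not depend on it. It is still worth correcting, because it is a flaw in a stated rule and cheap to repair.

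**What to change.** In SAP 6.1 (Secondary outcomes), replace the exclusion sentence with a rule that:

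1. keeps the primary-analysis denominator for <20 and <100;
2. for participants without a qualifying non-DBS viral load, codes a quantified DBS value at or above the threshold as not suppressed;
3. treats DBS results below the assay limit as indeterminate, and reports the comparison twice, with all of them coded suppressed and all coded not suppressed.

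The SAP has a model for step 3. For <400, section 6.2 codes undetected results on the high-limit Malawi platforms as suppressed and adds a sensitivity analysis with the opposite coding. The no-sensitivity-analysis clause in SAP 6.2 (Secondary outcomes analysis) needs a matching exception. The two codings bound the proportion in each arm; they are not the extreme values of the risk difference, and the text should say so.

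The cost is a few sentences and two extra runs, with no new data. The downside is that results at these thresholds appear as bounds wherever DBS is indeterminate.
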